#### 12.4.4 SAE Reporting

All serious adverse events (SAE) (including death and hospitalization), premature withdrawal, and emergency treatment disclosures must be reported to the Project Manager at the Lahey Hospital & Medical Center within one working day. Applicable SAE forms should be completed in the electronic data capture system (EDC) within 10 days of their occurrence and updated as new information becomes available.

Medical and scientific judgment should be exercised in deciding whether expedited reporting is appropriate in other situations, such as important medical events that may not be immediately life-threatening or result in death or hospitalization, but may jeopardize the subject or may require intervention. All deaths occurring on study must be reported to the Lahey Hospital & Medical Center. These include deaths within 30 days of the end of study visits.

### 13.0 Efficacy Variables

Primary and secondary efficacy variables are described below.

#### 13.1 Primary Variable

Time to residual/recurrent disease is defined as the time from the date of randomization until the date of residual/recurrent disease within the treated lesion(s). Any subject not known to have had residual/recurrent disease before transplant will be censored based on the last recorded date on which the

subject was still on study. The percentage of subjects who had residual/recurrent disease will also be derived.

### 13.2 Secondary Variable

To assess HRQL, subjects will be assessed using the Functional Assessment of Cancer Therapy—Hepatobiliary (FACT-Hep) Questionnaire (Appendix D). This 45-item self-report instrument is designed to measure HRQL in patients with hepatobiliary cancers and is one of the most widely-used instruments in this clinical area. The FACT-Hep consists of the 27-item FACT-G, which assesses generic HRQL, and the 18-item Hepatobiliary Subscale (HS), which assesses disease-specific issues such as pain, appetite, and cramping. The FACT-G is divided into four HRQL domains: physical well-being (7 items), social/family well-being (7 items), emotional well-being (6 items), and functional well-being (7 items). All items have a 7-day reference period and are scored from 0-4 (“not at all” to “very much”), with higher scores indicating better HRQL. Score ranges are 0-28 for physical well-being, 0-28 for social/family well-being, 0-24 for emotional well-being, 0-28 for functional well-being, and 0-72 for HS. All subscale scores from the FACT-G and HS can be summed together to create a total FACT-Hep score, with a possible range of 0-180. The FACT-Hep takes approximately 10 minutes to complete.

Subjects assigned to the SBRT arm will complete the FACT-Hep at baseline, at the time of the second fraction of the SBRT treatment, on the last day of treatment, 2 weeks after treatment, and at the time of follow-up scans at 3, 6, 9, 12, 15, 18, 21 and 24 months from randomization or until liver transplantation.

Subjects assigned to the TACE arm will complete the FACT-Hep at baseline, TACE treatment #1, 2 weeks after treatment #1, at TACE treatment #2, 2 weeks after treatment #2, at TACE treatment #3, and 2 weeks after treatment #3. The number of TACE treatments will vary from 1 to 3, so not all HRQL assessments will be collected for all subjects. The HRQL assessment at the time of the last TACE will serve as the HRQL assessment on the last day of treatment, while the HRQL assessment done 2 weeks after the last TACE assessment will serve as the 2 weeks after treatment assessment. HRQL will then continue to be collected at the time of follow up scans at 3, 6, 9, 12, 15, 18, 21 and 24 months from randomization or until transplantation.

## 14.0 Safety Variables

Adverse events will be captured throughout the study along with, physical exams and standard laboratory tests.

## 15.0 Statistical Considerations

This is a randomized, non-blinded, Phase III trial to characterize the safety and efficacy of individualized SBRT, compared to TACE, for subjects who have primary HCC. The trial endpoints are time to progression or residual disease in the treated lesion(s), number of retreatments, radiologic response, pathologic response, toxicity, and HRQL, overall survival, and 60 day post-transplant morbidity and mortality.

## 16.0 Sample Size

This study is sized for hypotheses testing of improved time to residual or recurrent disease within the previously treated lesion(s) due to SBRT versus TACE treatment arms in the overall population of patients who are eligible for liver transplant and are on the waiting list. It is believed that more than 50% of patients will receive a transplant within 2 years of listing, but that far fewer patients will receive

a transplant within 1 year of study begin. Therefore we base power calculations on one year follow up and a drop rate of 15%. Based on initial data, we estimate a median time to residual or recurrent disease of 134 days in the TACE group. Based upon these numbers and a hazard ratio of 0.6 for the SBRT relative to the TACE group, a two-sided test controlling the overall type 1 error to 5% requires a total of 161 events (i.e. residual/recurrent disease) and about 131 patients per treatment arm to achieve a power of 90%. To achieve a power of 80%, a total of 120 events and about 98 patients per treatment arm are required. These calculations are made accounting for follow-up on patients once every three months where the calculated HR of 0.6 for this discrete model corresponds roughly to a HR of 0.54 if recurrent disease could be measured on the continuous time scale (days).

**Table 7 Sample Size Calculation**

HR	Median time  TACE (days)	Median Time  SBRT (days)	Power (%)	Nb of Events	Nb of patients per arm
0.6	134	223	90	161	131
0.6	134	223	80	120	98

 Median time is the median time to residual or recurrent disease.

Recruitment period of 365 days, duration of study of 2 years, yearly dropout rate of 15% (following exponential distribution), alpha=5%, two-sided test.

## 17.0 Statistical Analysis

Baseline as well as post treatment measures will be summarized by descriptive statistics as appropriate such as mean, median, standard deviation, range and interquartile range. Comparison between treatment groups at baseline as well as changes from baseline will be made as appropriate using t-tests, Wilcoxon, chi-square and McNemar's tests as appropriate.

### 17.1 Primary endpoint

The primary analysis of the primary endpoint of time from randomization to residual or recurrent disease will be based upon the Kaplan-Meier estimates of time to event for the two groups where the two groups are compared using the log-rank test. Patients will be censored at time of transplantation or two years, whichever comes first. The primary analysis will treat patient death as residual or recurrent disease (effectively the compound endpoint of residual or recurrent disease or death). During the time frame of two years mortality should be low, but treatment of death as residual or recurrent disease is conservative. Secondary analyses using the Cox regression model will explore predictors of recurrence beyond group assignment, and also explore interactions between treatment and these other factors. We will also explore sex and treatment center differences. Secondary analyses will also censor for deaths unrelated to treatment. Statistical tests will be made at the two-sided 5% level.

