### 1.0 Primary endpoint:

Time from randomization to date of progression or residual disease of previously treated lesions as determined by the date of the radiologic imaging.

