## 3.0 Randomization Plan

All consented subjects will receive a Study Identification Number (SID) in the EDC system. The SID number will be a 4 digit number. The first two digits are site number. Site number will be assigned by the Coordinating Center at Lahey and it will start with 01 with 1 increment for each site (that is 01, 02, 03, etc.). The last two digits are the patient screening order starting from 01. Eligible subjects will be randomized after eligibility is confirmed by the provider, as soon as practical to the baseline tumor scan. Randomization will be performed using randomly selected block sizes of 2, 4 and 6 and stratified by the

following factors identified at screening: CTP score (either A or B) and disease etiology (with or without Hepatitis C). The randomization ID will be a 5 digit number in the form of ABCDE where, AB denote the site number, C indexes the four strata used for the randomization and DE index the order of screening at that site. C will be one of the numbers from 1 to 4. DE is the patient screening order starting from 01. Each study site will receive randomization list from the Coordinating Center at Lahey and randomize the eligible subjects individually. Site staff involved in randomizing subjects will not be aware of the randomization sequence before randomization. Randomization will be documented on both source document and EDC indicating assignment. If a patient is lost from the study because they are unable to receive their randomized treatment then an additional patient will be enrolled.(i.e., unable to meet SBRT dose constraints or achieve an acceptable respiratory motion strategy for SBRT). Individual randomization codes will be not be reused.

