### **5.2 Super-selective chemoembolization**

5.2.1 Once vascular supply of the tumor is identified super-selective chemoembolization of the tumor supplying artery is performed with catheter positioned in second or third order side branches. If the anatomy is sufficiently visualized with fluoroscopy, and a cone-beam CT is available, a cone-beam CT will be performed to assess appropriate segmental contrast distribution covering the target.

5.2.2 TACE will be performed with (see Appendix C). Two vials of beads will be prepared with, per the discretion of the treating physician, 50mg of Doxorubicin. Iodine contrast will be mixed

according to manufacturer guidelines and used to guide the delivery. Bead size will be at the discretion of the treating physician.

5.2.3 TACE without doxorubicin will be performed in an identical manner. Bead size will be at the discretion of the treating physician.

5.2.3 Target area will be embolized until segmental arterial stasis is achieved. In the presence of multifocal disease selective catheter positioning will be repeated for each lesion.

5.2.4 If available, final cone-beam CT will be performed to document distribution of the embolic material.

5.3 Following the TACE procedure all subjects will remain in hospital per standard of care for extended recovery.

5.4 If stasis of arterial flow to the tumor(s) was not achieved, additional TACE treatments will be administered, each approximately 4-6 weeks after the prior TACE procedure was performed until stasis is achieved with a maximum of three TACEs administered as initial therapy. After the first TACE, any additional treatments will be performed per the discretion of the treating Interventional Radiology Team.

**Completed treatment will be defined by the date of the final TACE procedure considered as part of initial therapy (up to 3 TACE treatments).**

5.5 Progression of disease will be confirmed with imaging done greater than 8 weeks from last treatment date. Images collected per transplant protocol within the 8 weeks of treatment will be repeated, as per study schematic, to confirm response to treatment or progression.

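### The primary log-rank leaves out the randomisation strata (a power matter only), and the protocol does not settle which scan dates an event, so failures can be dated at different delays in the two arms

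*Combined protocol and SAP*

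**What the plan says.** **Strata.** Section 3.0 (Randomization Plan) stratifies by "CTP score (either A or B) and disease etiology (with or without Hepatitis C"), which gives four cells. It adds that "Each study site will receive randomization list from the Coordinating Center at Lahey and randomize the eligible subjects individually". Section 17.1 compares the arms "based upon the Kaplan-Meier estimates of time to event for the two groups where the two groups are compared using the log-rank test" and names no strata. Cox regression appears only in exploratory form: "Secondary analyses using the Cox regression model will explore predictors of recurrence beyond group assignment".

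**Event date.** Section B 1.0 defines the endpoint as "Time from randomization to date of progression or residual disease of previously treated lesions as determined by the date of the radiologic imaging". So a scan date is used, but which scan is not stated. The related rules are these:
- Section 5.5, inside the TACE treatment plan: "Progression of disease will be confirmed with imaging done greater than 8 weeks from last treatment date". Transplant-protocol scans taken earlier "will be repeated, as per study schematic, to confirm response to treatment or progression".
- Section 5.6: in both arms, residual or recurrent disease in a treated lesion meets the endpoint whenever in follow-up imaging shows it.
- Section 7.0, Table 4: scans at 3 months ± 4 weeks and quarterly after that, with off-window scans allowed under transplant schedules.
- Section 11.1.3.4: first scan at four months ± 4 weeks for patients not on the transplant list.
- Section 11.1.4: response is assessed only after all planned TACEs. Section 5.4 allows up to three, about 4–6 weeks apart.

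**Other handling.** "Patients will be censored at time of transplantation or two years, whichever comes first". Death counts as an event, and a secondary analysis censors deaths unrelated to treatment. No sensitivity analysis for scan timing is named.

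**The concern.** The two gaps differ in kind. Leaving the strata out of the test ignores part of the design; if the strata are prognostic, some power is given away.

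The dating gap touches the comparison itself. A lesion that has already failed takes the date of its first countable scan, so a later first countable scan reads as longer control. TACE can run to three sessions and SBRT is over within 15 days (section 4.4.3.1), so that scan can fall at different times by arm even when the treatments are equally effective. The trial is unblinded (section 15.0), and a dating rule or sensitivity analysis chosen after results are known would carry little weight.

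**Working it through.** **1. The plan's own figure.** Section 16.0 gives HR 0.6, two-sided 5%, 120 events for 80% power and 161 for 90%. With 1:1 allocation, events = 4(z₀.₉₇₅ + z_power)² / (ln 0.6)². For 80%: 4 × 7.849 / 0.2609 = 120.3. For 90%: 4 × 10.507 / 0.2609 = 161.1. Both figures reproduce, with no allowance for strata or for arm-specific scan delay.

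**2. Strata.** From sections 16.0 and Table 7: 98 per arm, 365-day accrual, two-year study, 15% yearly dropout, TACE median 134 days. Assumed: CTP B 30%, hepatitis C 50%, the stratum hazard ratios, the TACE session mix, and 30% transplanted per year (1 − 0.7² = 51% by two years; section 16.0 expects more than 50%). Power is shown unstratified → stratified. Only the differences matter, because these runs use HR 0.6 in continuous time (see the objection).

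| Setting | Not prognostic | 1.5 and 1.5 | 2 and 1.5 |
|---|---|---|---|
| One session | 80.5 → 78.8 (−1.7) | 77.3 → 77.8 (+0.5) | 74.5 → 77.7 (+3.2) |
| 1/2/3 sessions in 50/30/20% | 75.2 → 72.9 (−2.3) | 70.0 → 69.6 (−0.4) | 64.8 → 67.2 (+2.4) |
| One session, no transplant | 87.0 → 86.0 (−1.0) | not run | 82.1 → 85.6 (+3.5) |
| 50/30/20%, no transplant | 82.3 → 80.5 (−1.8) | not run | 76.5 → 79.1 (+2.6) |

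A separate simulation gave −0.4 points (not prognostic) and +3.9 (2 and 1.5). With prognostic strata its unstratified test rejected a true null in 3.6–4.8% of trials, so there is no inflation. Adding site to the strata (10 sites assumed, 40 cells) cost a further 10–12 points there and 13–18 in the first simulation.

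**3. When scans begin to count.** Latest start, day 21 (section 7.0, Tables 2 and 3), plus treatment span, plus 56 days (section 5.5):
- one TACE: 21 + 0 + 56 = 77
- two: 21 + 42 + 56 = 119 (105 with a 4-week gap)
- three: 21 + 84 + 56 = 161 (133 with 4-week gaps)
- SBRT: 21 + 15 + 56 = 92, if the rule covers SBRT

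These are the days from which a scan counts after the latest start; the scan itself may come later. The month-3 window is 91 ± 28 = days 63–119, so day 161 lies outside it. The assumed TACE median of 134 days falls among these dates.

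**4. Effect under no treatment difference.** Inputs as in step 2, with scans every 91 ± 28 days and 3,000–4,000 trials per cell (Monte Carlo error about 0.3 points at 2.5%). Early scans are either repeated at 57–71 days after last treatment (prompt) or wait for the next visit. Entries are the percentage of null trials significantly favouring TACE (nominal 2.5%), without residual disease at first scan / with 25% residual.

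| 8-week rule, repeat | All one session | 70/20/10% | 50/30/20% | One third each |
|---|---|---|---|---|
| Both arms, prompt | 2.4 / 1.8 | 3.6 / 4.8 | 4.5 / 9.0 | 5.8 / 15.5 |
| TACE only, prompt | 2.2 / 2.5 | 3.6 / 5.9 | 4.4 / 9.9 | 5.3 / 15.7 |
| Both arms, waiting | 1.3 / 0.3 | 2.9 / 2.0 | 4.0 / 5.8 | 6.4 / 10.2 |
| TACE only, waiting | 3.8 / 6.5 | 8.1 / 17.1 | 12.8 / 28.0 | 15.4 / 40.9 |

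With both arms, waiting and one session, the tilt reverses: SBRT is favoured in 6.0% and 11.6% (null HR 0.94 and 0.88). For both arms, prompt, 50/30/20%, the null HR is 1.05 and 1.11. Separate re-runs of 700 trials gave 4.4–4.9% and 8.6–10.1% for that cell, 27.7–28.7% for the 28.0% cell, and 10.4–10.6% for the reversal with residual disease. If the first suspicious scan dates the event in both arms, the rate stays at 2.3–3.0%. That run assumes readable scans during the TACE course, which section 11.1.4 does not provide, so it shows only where the tilt comes from.

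**5. An analysis that respects the scan intervals.** An interval-censored proportional-hazards test had null HR 0.99–1.01 and 1.2–4.3% per side over 35 null scenarios (600–800 trials each).

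**The case against.** - **Stratifying is optional.** The unstratified test is valid, and the documents give no prognostic strength. This stands: it is a minor alignment of analysis with design. A reader might infer that omitting the strata inflates type I error; step 2 shows that it does not. Site lists arguably make site a stratum too, but the power cost argues against adding it.
- **Power.** A reader might infer that dating delays push power below 80%. The documents do not support that. Section 16.0 says its HR of 0.6 belongs to the quarterly model and corresponds to about 0.54 in continuous time. At 0.54, with prompt repeats in both arms and no residual disease, simulated power is 91.4, 89.1, 89.0 and 85.7% across the four mixes.
- **The 8-week rule probably covers both arms.** Section 5.5 speaks of treatment rather than TACE, and 5.5–5.8 go on to deal with both arms. This is a fair reading, though the rule sits under a TACE heading. The 28.0% and 40.9% figures need TACE-only scope, waiting, many repeat sessions and 25% residual disease together, so they should not be quoted as the expected effect.
- **Direction.** A reader might infer a bias against SBRT. The documents give neither session mix nor residual share, and one reading favours SBRT.
- **Transplant assumption.** Section 16.0 expects far fewer transplants within one year than within two; a constant 30% per year puts 30/51 = 59% of the two-year total in year one. This limits the precision of the figures but does not close the textual gap.

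**Conclusion.** Both parts hold, with different weight.

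The strata are a question of power only: about 1 to 3 points lost by stratifying if they are not prognostic, about even or a small gain at 1.5 and 1.5, and about 2 to 4 points gained at 2 and 1.5, all on assumed prevalences and effects.

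The dating gap is the reason to act. The sections listed do not give one rule, and the protocol's own timings allow the first countable scan to differ by arm. On the assumed 50/30/20% mix, with prompt repeats and the rule on both arms, null trials favour TACE in about 4–5% without residual disease and 9–10% with 25% residual. At that mix the rate is clearly higher only if the rule covers TACE alone and early scans wait. More repeat sessions raise it; with one session in both-arm waiting, the tilt favours SBRT. Size and direction therefore cannot be fixed from the documents. Confidence is medium: the gap in the text is certain, its effect depends on assumed inputs. It should be fixed before results are seen.

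**What to change.** 1. Make the primary log-rank, and the Cox model that supplies the hazard ratio, stratified by CTP class × hepatitis C, without site. State the small power cost if the strata are not prognostic.
2. Reconcile sections 5.5, 5.6, 7.0 (Table 4), 11.1.3.4 and 11.1.4. State which arms the 8-week imaging rule covers, when a scan first counts, when an early scan is repeated, and whether the suspicious or the confirming scan dates the event. One stated scan should date the event under the same rule in both arms.
3. Keep the primary test on scan dates and prespecify one interval-censored proportional-hazards sensitivity analysis: event between the last clean and the first positive valid scan, residual disease at the first valid scan left-censored, deaths at exact dates. A log-rank on a common visit grid from month 6 is not a good substitute: in simulation it dropped 34–39 of 196 patients and tied 69–81% of events at month 6.
4. Report by arm the day of the first valid scan, the number of TACE sessions and the share with residual disease at that scan.

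The cost is protocol and SAP wording plus standard software. Strata and scan dates are already collected, the sample size is unchanged, and the sensitivity analysis takes no power from the primary test.

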## Protocol Synopsis

Title	A Randomized Multicenter Phase III Study of Individualized Stereotactic Body Radiation Therapy (SBRT) versus Trans-Arterial Chemoembolization (TACE) as a Bridge to Transplant in Hepatocellular Carcinoma.
Objective	
Primary:
 
 
• To compare the duration of disease control in treated lesions when utilizing SBRT versus TACE as a bridging strategy for patients with HCC eligible for liver transplantation.
 
 
Secondary:
 
 
• To determine health related quality of life (HRQL) for both treatment arms
 
• To compare toxicity
 
• To compare number of further interventions
 
• To compare pathologic response of treated lesion(s).
 
• To compare radiologic response of treated lesion(s).
 
• To assess 60 day Post-transplant morbidity and mortality
 

Study Design	A multicenter prospective randomized phase III trial
Sample Size	196 subjects will be enrolled

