## **D. RESEARCH DESIGN AND METHODS**

### **1.0 Eligibility**

#### **1.1 Inclusion Criteria**

- Subjects with HCC are eligible for this trial. HCC is defined as having at least one of the following:
  - Biopsy proven HCC or:
  - A discrete hepatic tumor(s) as defined by the Barcelona (29) criteria for cirrhotic subjects,  $\geq$  2cm with arterial hypervascularity and venous or delayed phase washout on CT or MRI.
- Subjects are liver transplant candidates (actively awaiting organ transplant per transplant services in documentation), or, potential liver transplant candidates (at the discretion of the liver team and/or Principal Investigator) advised by liver transplant services as needing local treatment prior to liver transplant evaluation.
- Subjects must be within UCSF criteria (one solitary tumor smaller than 6.5 cm, or patients having 3 or fewer nodules, with the largest lesion being smaller than 4.5 cm or having a total tumor diameter less than 8.5 cm without vascular invasion) and eligible for potential liver transplant.
- Subjects must be eligible for standard TACE and SBRT procedures.
- Subjects must have a life expectancy of at least 12 weeks.
- Subjects must be 18 years of age or older. Adult subjects of all ages, both sexes and all races will be included in this study.
- Subjects must sign an informed consent form approved for this purpose by the Institutional Review Board (IRB) of record.
- Subjects must have a Child-Turcotte-Pugh (CTP) score  $\leq 8$ .
- Patients must have adequate organ function within 2 weeks of enrollment.
  - Bone marrow: Platelets  $\geq 30,000/\text{mm}^3$
  - Renal: BUN  $\leq 40 \text{ mg/dl}$ ; creatinine  $\leq 2.0 \text{ mg/dl}$
  - Hepatic: INR  $\leq 1.5$  or correctable by Vitamin K, unless anti-coagulated for another medical reason
  - Bilirubin  $< 3.0 \text{ mg/dl}$  (in the absence of obstruction or pre-existing disease of the biliary tract, e.g. primary sclerosing cholangitis).
- Patients' uninvolved liver volume will be estimated and must be  $> 700\text{ml}$ .
- Patients must have a Zubrod performance status of  $\leq 2$ .
- Patients who are sexually active must agree to the use of contraception throughout the duration of the study.

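### The primary log-rank test ignores the number of treated lesions, which randomisation does not balance: an avoidable inefficiency and an unprotected chance imbalance

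*Combined protocol and SAP*

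**What the plan says.** - **Endpoint.** Section 13.1 counts time from randomisation "until the date of residual/recurrent disease within the treated lesion(s"). Section 5.6 takes a patient off study once residual disease or local recurrence is seen in treated lesion(s), and section 11.2 classifies each treated lesion separately.
- **Eligibility.** Section 1.1 admits a solitary tumour under 6.5 cm, or "patients having 3 or fewer nodules, with the largest lesion being smaller than 4.5 cm" or with total diameter under 8.5 cm.
- **Randomisation.** The strata in section 3.0 are "CTP score (either A or B) and disease etiology (with or without Hepatitis C"). Tumour burden is not among them.
- **Primary test.** Section 17.1 gives Kaplan-Meier estimates "for the two groups where the two groups are compared using the log-rank test". Cox models are secondary and exploratory. Lesion number is not named in them.
- **Sample size.** Section 16.0 uses "a two-sided test controlling the overall type 1 error to 5" per cent, "a hazard ratio of 0.6 for the SBRT relative to the TACE group", and a TACE median of 134 days taken from initial data. It states: "To achieve a power of 80%, a total of 120 events and about 98 patients per treatment arm are required". The Synopsis takes that option: "196 subjects will be enrolled".

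**The concern.** A patient with three treated lesions has three places where the event can occur, and a patient with one lesion has one. If that raises the patient-level hazard, lesion number is a prognostic factor built into the endpoint.

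Leaving such a factor out of a log-rank test has two consequences. First, if treatment multiplies the hazard by a constant within each lesion-number group, the hazard ratio over the mixed population lies nearer 1 than the within-group ratio, so the unstratified test is less powerful than a stratified one. Second, nothing holds the share of multi-lesion patients equal between arms. An unlucky allocation would shift the primary estimate, and section 17.1 offers only an exploratory model with unnamed predictors in response. In a trial that section 15.0 describes as non-blinded, an adjustment chosen after such an imbalance is noticed would be hard to defend.

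**Working it through.** **1. The plan's own figure.** Inputs from section 16.0 and Table 7: two-sided 5%, hazard ratio 0.6, 98 patients per arm. By Schoenfeld's formula:

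- Events = 4 × (1.960 + 0.842)² / (ln 0.6)² = 4 × 7.849 / 0.2609 = 120.3.
- Power at 120 events = Φ(√120 / 2 × 0.5108 − 1.960) = Φ(0.838) = 79.9%.

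The 80% row is reproduced, and so is the 90% row (161 events give 90.0%). The calculation applies to an unadjusted log-rank whose average hazard ratio is 0.6.

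**2. Power at 120 expected events if 0.6 is instead the within-group ratio.** Assumptions that are not in the documents: lesion mixes (1/2/3 lesions) of 70/20/10, 60/30/10 and 50/30/20%, and the relative hazards below. The TACE median is held at 134 days and times are continuous. Each scenario has 6,000 simulated trials; the Monte Carlo standard error is about √(0.8 × 0.2 / 6,000) = 0.5 points per power figure. Stratification here uses all three lesion counts. With no heterogeneity, simulated power is 79.5%.

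| Relative hazard, 1/2/3 lesions | Unstratified | Stratified | Gain (points) | Hazard ratio implied by unstratified power |
|---|---|---|---|---|
| 1/1.3/1.6 | 78.3-78.5% | 78.5-79.1% | 0-1 | 0.605-0.606 |
| 1/1.5/2 | 77.0-77.1% | 78.5-79.0% | 1-2 | 0.610-0.611 |
| 1/2/3 | 72.5-73.7% | 78.1-78.5% | 5-6 | 0.623-0.627 |

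**3. The same question under Table 7's accrual, duration and dropout**, assuming also that 50% are transplanted by two years and stratifying as 1 vs 2 or more (4,000 trials per scenario):

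- Hazards 1/2/3: unstratified 74-77%, stratified 81-82%, a gain of 5-7 points.
- Hazards 1/1.5/2: unstratified 79-81%, stratified 81-83%, a gain of 2-3 points.
- Lesion number irrelevant (60/25/15 mix): unstratified 84.1%, stratified 83.5%, a loss of 0.6 points.

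Type I error was about 5% with and without stratification. Power levels differ from step 2 because this set-up does not fix the events at 120, so the gains are the figures to compare. Neither set-up reproduces the three-monthly discrete model in section 16.0, which is not specified closely enough.

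**4. Chance imbalance.** With 98 per arm and a multi-lesion share p, the standard deviation of the between-arm difference is √(2p(1 − p) / 98):

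- p = 0.3: √(0.42 / 98) = 6.5 percentage points.
- p = 0.5: √(0.50 / 98) = 7.1 percentage points.

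In the step 3 simulations, each 10-point imbalance moved the unstratified log hazard ratio by about 0.05-0.08, a factor of exp(0.05) = 1.05 to exp(0.08) = 1.08. The stratified estimate moved by less than 0.005. SBRT had over 7 points more multi-lesion patients in about 14-19% of trials. In those trials:

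- Hazards 1/1.5/2: unstratified power was about 68-72%.
- Hazards 1/2/3: unstratified power was about 60-63%.
- Stratified power stayed near 79-83% in both.

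An imbalance the other way would flatter SBRT.

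**The case against.** A reader might infer that the stated 80% power is eroded. The documents do not support that. Section 16.0 gives a single hazard ratio for the two arms and a whole-arm median, and makes neither conditional on lesion number. If 0.6 is the average ratio that the test sees, power at 120 events is 79.9% and nothing is lost against the stated figure. The unstratified powers in step 2 fall short of it only because they treat 0.6 as the within-group ratio.

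The other objections vary in weight.

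- **Assumed inputs.** No lesion mix or hazard by lesion number is given. The largest gain needs hazard strictly proportional to lesion count. Eligibility works against that, since solitary tumours may be larger than any one of several nodules. Section 17.1 also counts death as an event, and death need not rise with lesion count. This stands, and it is why a range is given.
- **Validity.** An unadjusted log-rank is a legitimate primary test, and its 5% error rate already averages over chance imbalances. This stands. It does not help the reader of one trial in which an imbalance has occurred.
- **Inference from the text.** That failure of any one lesion is the event follows from sections 5.6 and 11.2, although the mRECIST table in Appendix B uses a sum over target lesions. Three eligible nodules need not mean three treated ones. Lesion count is needed for eligibility, but it is not listed as a data item. These points stand as cautions.
- **Priority.** The plan does not say whether the log-rank uses its two randomisation factors, which is a more direct gap. This is true, and both can be settled in one edit.

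**Conclusion.** The point holds as an efficiency and robustness issue. It is not an error in the power calculation or a threat to type I error. A baseline factor that is probably prognostic, and that eligibility imaging should make known before randomisation, is left out of both the allocation and the primary test.

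The average benefit of using it is modest: about 0-3 points of power for mild to moderate heterogeneity, 5-7 points in the extreme proportional case, and a loss of under 1 point if lesion number is not prognostic. Protection against an unlucky allocation is the stronger reason, and it does not depend on whether 0.6 is read as marginal or conditional. The absolute powers in the simulations do depend on that reading, and every size depends on the assumed lesion mix and hazards. Having chosen the 80% option, the trial has little slack, so a change this cheap should be made.

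**What to change.** Amend section 17.1 before outcome data are seen:

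1. Stratify the primary log-rank by number of target lesions on baseline imaging (1 vs 2 or more), fixed before randomisation.
2. Name lesion number and largest lesion diameter as covariates in the Cox model that reports the treatment hazard ratio.
3. Keep the unstratified log-rank as a sensitivity analysis.
4. Confirm that lesion count is captured as a baseline data field.
5. In the same edit, say whether the two randomisation factors enter the primary test.

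The cost is a documented change to the primary analysis and possibly one data field; no extra patients or scans are needed. The reported hazard ratio becomes conditional on lesion number rather than marginal, which should be stated because the sample size used a ratio not conditioned on it. If lesion number proves irrelevant, the power loss is under 1 point.
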